9.4.1 GENERAL APPROACH

In initial intention-to-treat analyses, all available data will be included. Multiple imputation will be used where dependent variable values are missing. In subsequent per-protocol analyses, only subjects with complete data will be included.

SAS (SAS Institute, Cary NC) 9.4 statistical software will be used.

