Follow-up visits will be scheduled on approximately POD 30 (Visit 11) and POD 90 (Visit 12). The exact timing of the follow-up visits is not strict and may occur up to ± 1 week from the proposed POD.

1 Month Follow-Up (Visit 11, approximately POD 30) and 3 Month Follow-Up (Visit 12, approximately POD 90)

- Record adverse events since last study visit, if applicable.
- Obtain standardized digital photographs of periauricular incisions/scars for visual analogue scale (VAS) scoring.
- Measure physical scar characteristics using OCT and three-dimensional skin imaging analysis.
- Measure collagen and water concentration using a spatially resolved spectroscopy probe.
- Measure scar pliability using indentation instruments to quantify skin elasticity and induration.
- Perform subjective scar evaluation using the Patient and Observer Scar Assessment Scale (POSAS). The observer assessment is done by a blinded investigator (the treating surgeon).

At the 1 month follow-up visit, optional post-treatment skin biopsies will be obtained if the subject has provided consent. Subjects may decline biopsy and remain in the study.

Final Study Visit (Visit 13, approximately POD 180): Same procedures/evaluations as previous visit, plus an exit questionnaire to elicit the subject's feedback.

The final study visit is a 6-month follow-up at approximately POD 180. However, subjects will have the option to attend a 12-month follow-up (approximately POD 365) that consists of the same procedures/evaluations as the previous visit. While a study endpoint at 12 months would be ideal for long-term monitoring of clinical changes during the scar maturation process, subject attrition is a concern and we anticipate that subjects may have difficulty returning to clinic 1 year post-surgery.

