9 STATISTICAL CONSIDERATIONS

9.1 STATISTICAL HYPOTHESES

- Hypothesis for Primary Efficacy Endpoint: There is a statistically significant difference in scar pliability between a LED-RL-treated incision and a mock-treated incision.
 - Skin elasticity and induration (an index of scar pliability) are measured pre-treatment at the first treatment session and post-treatment on follow-up visits at POD 30, 90, and 180.
- Hypothesis for Secondary Efficacy Endpoint(s): LED-RL phototherapy treatment results in a statistically significant improvement in POSAS score and VAS score compared to mock treatment.

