9.2 SAMPLE SIZE DETERMINATION

The study will have three treatment arms (LED-RL 160 J/cm², LED-RL 320 J/cm², and LED-RL 480 J/cm²) with 10 subjects each. The primary outcome measure is the difference in pliability between a treated incision site and the contralateral mock-treated incision site.

To calculate the sample size for this study, we anticipate that the minimal clinically important difference in scar pliability is 15%, based on minimum decrease in fibroblast cell number after LED-RL treatment from our *in vitro* data. A power analysis plan predicted that with 9 subjects, the study would have greater than 80% power to detect a 15% difference in pliability by using a two-sided paired *t*-test. To take into account a dropout rate of 10%, 10 subjects will be enrolled in each treatment arm. Up to 150 potential participants will be screened and a total of 30 subjects will be enrolled in the study.

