9.3 POPULATIONS FOR ANALYSES

- Intention-to-treat (ITT) analysis dataset: all participants who are enrolled and randomly allocated to treatment, regardless of treatment actually receive
- Per-protocol analysis dataset: participants who adhered to the protocol and completed the treatment originally allocated (i.e., attended all treatment sessions)
- Safety analysis dataset: participants who received at least one dose of the study intervention

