9.4.2 ANALYSIS OF THE PRIMARY EFFICACY ENDPOINT(S)

The two principal outcomes (scar pliability measurements of skin elasticity and skin induration) will be used separately as dependent variables (DVs) in mixed linear models. Fixed factors in each model will be treatment group, whether treated, side of face (left versus right), and time (3 points post-baseline). Baseline DV measure will be introduced as a scored covariate; subject ID as a random factor. The Akaike information criterion will be used to assess what intra-subject covariance structure might be optimal. Tests of Interaction among fixed factors will be conducted, and the utility of polynomial terms in the baseline DV investigated. Model residuals will be examined for skew and for outliers; the DV will be power-transformed if necessary to maximize normality of residuals.

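### Section 9.4.1 restricts the per-protocol analyses to subjects with complete data, a filter that is absent from the Section 9.3 definition and that the planned mixed model does not need

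*Combined protocol and SAP*

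**What the plan says.** The points below are all from the combined protocol and SAP.

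- **Section 9.3** defines the per-protocol dataset as "participants who adhered to the protocol and completed the treatment originally allocated (i.e., attended all treatment sessions"). It sets no condition on outcome data.
- **Section 9.4.1** describes the intention-to-treat analysis first. It includes all available data, and "Multiple imputation will be used where dependent variable values are missing". It then says: "In subsequent per-protocol analyses, only subjects with complete data will be included". The sentence does not define complete data and does not refer to the Section 9.3 set.
- **Section 9.4.2** gives the primary analysis. Elasticity and induration "will be used separately as dependent variables (DVs) in mixed linear models", with subject as a random factor, the baseline value as a covariate, and fixed factors that include "side of face (left versus right), and time (3 points post-baseline").
- **Section 9.1** gives the timing. Elasticity and induration "are measured pre-treatment at the first treatment session and post-treatment on follow-up visits at POD 30, 90, and 180".

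**The concern.** The per-protocol analysis has two membership rules. One concerns treatment received and the other concerns data obtained. A subject can satisfy the first and fail the second, because baseline is measured at the first treatment session while the other three readings come at follow-up visits after the ninth.

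Two things are at stake. First, readings that were taken on fully treated subjects would be thrown away, although the planned model accepts an incomplete series. Second, the comparison between the two analyses becomes hard to read. The usual purpose of a per-protocol analysis is to show what changes when only adherent subjects are kept. Here the analyses would also differ in how missing readings are handled: all data plus imputation in one, deletion of whole subjects in the other. The deletion would further select, after randomisation, against subjects who finished treatment and left during follow-up.

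**Working it through.** **The plan's own figure.** Section 9.2 requires 9 subjects per arm and allows for 10% dropout: 9 / (1 − 0.10) = 10 per arm, 30 in total. This reproduces. Conversely, 10 × 0.90 = 9 remain per arm if that dropout is the only loss.

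**One subject under the two rules.** Inputs are two sides of the face and three post-baseline times (Section 9.4.2), counting one reading per side, visit and instrument.

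- Scheduled post-baseline readings per instrument: 2 × 3 = 6.
- Lost with one missed follow-up visit: 2 × 1 = 2, so 6 − 2 = 4 are observed.
- Used if the Section 9.3 set enters the mixed model with all available readings: 4 of 6.
- Used under the Section 9.4.1 sentence: 0 of 6.

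**How many subjects.** The documents give no rate of missed follow-up visits, so a range is assumed. Let m be the probability of missing any one follow-up visit, independent across the three visits, among subjects who attended every session.

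- Complete subjects: (1 − m)³.
- Share of observed readings discarded: 1 − (1 − m)³ / (1 − m) = 1 − (1 − m)².

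| m (assumed) | Complete, (1 − m)³ | Expected complete of 10 | Observed readings discarded |
|---|---|---|---|
| 2% | 0.98³ = 0.941 | 9.4 | 1 − 0.98² = 4% |
| 5% | 0.95³ = 0.857 | 8.6 | 1 − 0.95² = 10% |
| 10% | 0.90³ = 0.729 | 7.3 | 1 − 0.90² = 19% |

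The base of 10 supposes that everyone randomised to the arm attended all nine sessions. If the missing visits cluster in the same subjects, as they do with outright dropout, fewer subjects are affected for the same number of missing readings.

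**The case against.** The best defence is that the two sections can be reconciled. Section 9.4.1 may be a further restriction within the Section 9.3 set, or adherence to the protocol may be meant to include follow-up visits. A reader might infer a flat contradiction, and the text does not support that. However, neither reconciliation is written down. The explanatory phrase in Section 9.3 mentions treatment sessions only. If the filter is a further restriction, the set defined in Section 9.3 is never analysed as defined.

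The defence is also right that the per-protocol analysis follows an intention-to-treat analysis that keeps everything, and that a completers run can serve as a contrast to the imputed result. The plan also works to limit missed visits: windows of one week either way (Section 1.3), reminders (Section 5.5) and rescheduling (Section 7.3). These points limit the size of the problem but give no reason for the filter.

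Three stronger inferences should be set aside.

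- *Subjects who decline the biopsy would be excluded.* Section 1.3 says "Subjects may decline biopsy and remain in the study", so the biopsy is not required data. The sentence before the filter concerns dependent variables, a term that Section 9.4.2 uses for elasticity and induration. The natural reading is completeness of the analysed outcome.
- *The filter takes the trial below its stated power.* Section 9.2 claims that "with 9 subjects, the study would have greater than 80% power to detect a 15% difference in pliability", for a paired t-test and with no standard deviation or significance level. No power is claimed for the per-protocol analysis, and the planned model pools sides, times and arms. A power loss cannot be derived from these documents.
- *The filter removes subjects withdrawn during treatment for a reaction or a worsening scar.* Those subjects have not attended all sessions and already fall outside Section 9.3. Only losses after the ninth session are due to Section 9.4.1.

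**Conclusion.** The point holds for the per-protocol analyses only. Section 9.4.1 imposes a complete-data condition that Section 9.3 does not contain and the mixed model does not need. For a fully treated subject with one missed follow-up visit, the cost is certain: zero of six post-baseline readings per instrument are used instead of four. For the trial as a whole the cost is unknown. It ranges from about 6% to 27% of fully treated subjects if follow-up visits are missed independently at 2% to 10% each. It is one subject in ten per arm at most if the planned dropout is the only loss, and nothing if those dropouts also missed treatment sessions.

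Interpretation matters more than precision here. As written, a gap between the intention-to-treat and per-protocol estimates could not be attributed to adherence. A reader might infer that the primary result is compromised. It is not, because no intention-to-treat estimate or test is touched. The change should be made, but it concerns a supportive analysis.

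**What to change.** Replace the Section 9.4.1 sentence with:

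> *Per-protocol analyses use the per-protocol set of Section 9.3 and fit the same mixed model to all available post-baseline readings of those subjects; no subject is removed for a missing follow-up reading.*

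If a completers analysis is wanted, keep it as a labelled sensitivity analysis and state which readings must be present. If attendance at follow-up visits is meant to be part of adherence, say so in Section 9.3, so that membership is defined in one place.

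The replacement covers post-baseline readings only. A failed baseline reading would still need its own rule, because baseline is a covariate in the model.

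The cost is one sentence in the plan, with no additional data, visits or programming beyond the model already specified. It is best settled before results are seen, since the undefined term otherwise leaves the choice of dataset open.

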9.4.2 ANALYSIS OF THE PRIMARY EFFICACY ENDPOINT(S)

The two principal outcomes (scar pliability measurements of skin elasticity and skin induration) will be used separately as dependent variables (DVs) in mixed linear models. Fixed factors in each model will be treatment group, whether treated, side of face (left versus right), and time (3 points post-baseline). Baseline DV measure will be introduced as a scored covariate; subject ID as a random factor. The Akaike information criterion will be used to assess what intra-subject covariance structure might be optimal. Tests of Interaction among fixed factors will be conducted, and the utility of polynomial terms in the baseline DV investigated. Model residuals will be examined for skew and for outliers; the DV will be power-transformed if necessary to maximize normality of residuals.

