6.3 MEASURES TO MINIMIZE BIAS: RANDOMIZATION AND BLINDING

Treatment Dose Randomization

A block randomization scheme will be used for balanced allocation of subjects to study arms, such that 10 subjects are assigned to each treatment group. All subjects will be randomized as they are enrolled

(i.e., sequentially in blocks of three). Study enrollment concludes when a total of 30 subjects have been randomized.

For the first subject who enrolls, Arabic numeral "1", "2", or "3" will be generated at random using a computer-based randomization tool (*www.randomizer.org*). This subject has a 1 in 3 chance of being assigned to any of the three treatment groups: "1" for Group 1 (LED-RL 160 J/cm²), "2" for Group 2 (LED-RL 320 J/cm²), or "3" for Group 3 (LED-RL 480 J/cm²). The next subject who enrolls is then similarly randomized to one of the remaining two treatment groups, and the following subject who enrolls is automatically assigned to the last treatment group. This block randomization process continues until each treatment group is filled with 10 subjects.

Split-Face Randomization

Within each treatment group, the treatment side (right face versus left face) will be determined using a computer-generated randomization tool (*www.randomizer.org*). The assignment to a treatment dose and a treatment side of the face occurs simultaneously. Within each treatment group, a single set of Arabic numerals "0" to "9" will be generated, resulting in a random sequence of 10 numerals for sampling without replacement. As subjects are allocated to a treatment group, they are assigned to a numeral in this set based upon their order of enrollment. In other words, the first subject to enroll in a treatment group is assigned to the first random numeral, the second subject to the second random numeral, etc. Subjects assigned to even numerals will receive LED-RL phototherapy on the right side of the face, making the left face the control. Subjects assigned to odd numerals will receive LED-RL phototherapy on the left side of the face, making the right face the control. Within each treatment group (n=10), 5 subjects will receive treatment on the right face and the other 5 subjects will receive treatment on the left face.

Blinding

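### Section 9.4.2 does not require the primary model to link the three visits on one side of the face, so an analyst could follow the plan and still get an anti-conservative treated-versus-mock test.

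*Combined protocol and SAP*

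**What the plan says.** Section 9.4.2 fits a mixed linear model to elasticity and another to induration. On the fixed part it says: "Fixed factors in each model will be treatment group, whether treated, side of face (left versus right), and time (3 points post-baseline"). On the rest it says: "Baseline DV measure will be introduced as a scored covariate; subject ID as a random factor", and then: "The Akaike information criterion will be used to assess what intra-subject covariance structure might be optimal". It lists no candidate structures. It does not say whether the repeated unit is the subject or the side within the subject, and it names no degrees-of-freedom method.

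Section 6.3 randomises the treated side within each subject. In each dose group of 10, "5 subjects will receive treatment on the right face and the other 5 subjects will receive treatment on the left face". Section 9.2 bases the sample size on the subject's treated-minus-mock difference: "with 9 subjects, the study would have greater than 80% power to detect a 15% difference in pliability by using a two-sided paired" t-test.

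**The concern.** The side within a subject is the unit that receives LED-RL or mock, and each subject contributes 2 sides × 3 visits = 6 readings. A random subject intercept makes all six equally correlated, whether they come from the same side or opposite sides. It cancels out of the treated-minus-mock contrast, so it cannot supply that contrast's error term.

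The fixed effect for side removes the average left-right difference across subjects. It does not remove a difference peculiar to one subject, such as one incision under more tension or healing more slowly. If that difference persists over visits and the model has no term for it, three readings of one scar act as three replicates of the treatment comparison. The standard error is then too small, and side-to-side variation could be reported as an effect on pliability. The paired t-test in section 9.2 does not have this weakness, because its error term is the spread of the paired difference across subjects.

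**Working it through.** **Inputs from the documents.** 30 subjects, 10 per dose group (9.2); two sides, with 5 right and 5 left treated per group (6.3); three post-baseline visits (9.4.2).

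**Assumptions.** Two-sided alpha of 0.05, since no level is stated. The side-specific share of within-subject variance, ρ, is not given, so a range is used.

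**The plan's own figure.** The dropout step reproduces: 9/(1 − 0.10) = 10 per arm, 30 in total. The power statement cannot be checked, because no SD is given. At the assumed alpha, 9 subjects reach 80% only if the SD of the paired difference is at most 15/1.067 = 14.1 percentage points.

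**Variance of the contrast.** Let σ²s be the variance of the side-within-subject effect, σ²e the visit-level residual variance, and k = σ²s/σ²e = ρ/(1 − ρ).

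- True variance of one subject's treated-minus-mock difference, averaged over three visits: 2(σ²s + σ²e/3) = (2σ²e/3)(1 + 3k).
- With a subject intercept and independent residuals, error is pooled over about five within-subject degrees of freedom per subject. One has expectation σ²e(1 + 3k) and four have σ²e, so the model uses about (2σ²e/3)(1 + 0.6k).
- Understatement factor: V = (1 + 3k)/(1 + 0.6k). Ratio of model SE to true SE: 1/√V. Large-sample type I error: 2[1 − Φ(1.96/√V)].

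| Share ρ | k | V | SE ratio | Error, formula | Error, simulated (N = 30) |
|---|---|---|---|---|---|
| 10% | 0.111 | 1.333/1.067 = 1.25 | 0.89 | 0.080 | 0.080 |
| 25% | 0.333 | 2.0/1.2 = 1.67 | 0.77 | 0.129 | 0.129 |
| 50% | 1.0 | 4.0/1.6 = 2.5 | 0.63 | 0.215 | 0.218 |

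The simulations used 200,000 null trials at 10% and 50%, and 20,000 at 25%. At ρ = 0 the simulated error is 0.050. With a side-within-subject term it is 0.049 to 0.051 at every share tried from 0 to 70%.

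**What the AIC step does.** The answer depends on the candidates, which the plan does not list.

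- Only compound symmetry and AR(1) over the six readings: about 8, 10 and 16% at shares of 10, 25 and 50%. Such fits are less precise than the table; a separate 400-run check gave 9.8% and 12%, with Monte Carlo error of about ±3 points.
- Subject only against subject plus side-within-subject, 30 subjects: 0.047, 0.063, 0.062, 0.056, 0.049 and 0.049 at shares of 0, 10, 20, 30, 50 and 70%. AIC picks the side term in 32% of trials at a share of 10% and in 68% at 20%.
- The same choice in one dose group of 10: 0.047 to 0.084, with the peak at a share of 30%, where AIC picks the side term in 52% of trials.

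**What the baseline covariate does.** If baseline enters separately for each side and fully carries the side effect, the subject-only error is 8.0, 11.1 and 16.2% at shares of 10, 25 and 50%. If baseline does not carry it, the error is 8.0, 13.0 and 22.5%.

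**The case against.** The strongest reply is that the plan nowhere specifies independent residuals. Directly after naming subject ID, it provides for an AIC-selected intra-subject covariance. A reader might infer from the random-factor clause alone that repeated visits count as independent evidence and that the planned test is anti-conservative. The documents do not support that. Even the literal random intercept implies compound symmetry rather than independence, and a sensible candidate list would bring the error close to nominal at 30 subjects. This part of the reply stands.

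The side fixed effect and the baseline covariate also remove some left-right variation. That stands in part: a per-side baseline lowers the error at the larger shares, but at best to about 8, 11 and 16%.

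Section 4.2 takes it as given that, untreated, the two sides would scar alike. If that held exactly for every subject and the measurements added no lasting side difference, the share would be zero and nothing would be lost. It is an assumption without supporting data, and the primary test need not depend on it.

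The paired t-test was a planning tool, and a mixed model need not reproduce it. That is also fair. The model does still need an error term at the level of the randomised unit.

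**Conclusion.** The point holds as a conditional one. Section 9.4.2 permits a model with no side-within-subject component. If such a model is used and sides differ persistently within subjects, the primary test rejects too often: about 8, 13 and 22% with a subject intercept alone at shares of 10, 25 and 50%, and about 8, 10 and 16% with AIC restricted to compound symmetry and AR(1). If a side structure is a candidate, the error is about 5 to 6% at 30 subjects and at most about 8% in one dose group.

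These figures rest on a two-sided 5% level and a variance share that the documents do not give. It would go too far to say that the planned standard errors are too small, because the final structure is left open. The point is still more than a missing detail, since two analysts could both comply with 9.4.2 and obtain tests with materially different error rates.

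**What to change.** In 9.4.2, fix the minimum covariance structure before data are analysed: a random subject effect plus a random side-within-subject effect, or an equivalent covariance with visits repeated within subject-by-side. Name a small-sample degrees-of-freedom method such as Kenward-Roger. Restrict AIC to choosing the visit-to-visit correlation within a side, and list the candidates. State also that baseline enters separately for each side.

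This needs a sentence or two of wording, with no change to design or data collection. The cost is somewhat wider confidence intervals. Relative to a subject-only model the standard error grows by √V, that is by 1.12, 1.29 or 1.58 at shares of 10, 25 or 50%, which is the understatement being removed. At a share of zero the main cost is fewer degrees of freedom for the contrast: about 28 (30 − 2) rather than 146 (28 + 118) in the simplified model used here.
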